Appendix 3 **Procedures for Recording Adverse Events**

Investigators should use correct medical terminology/concepts when recording adverse events on the Adverse Event eCRF. Avoid colloquialisms and abbreviations.

Only one AE term should be recorded in the event field on the Adverse Event eCRF.

1. DIAGNOSIS VERSUS SIGNS AND SYMPTOMS

1.1. INFUSION-RELATED REACTIONS

AEs that occur during or after study drug administration and are judged to be related to study treatment infusion should be captured as a diagnosis (e.g., "infusion-related reaction" and "anaphylactic reaction") on the Adverse Event eCRF. If possible, avoid ambiguous terms such as "systemic reaction". Associated signs and symptoms should be recorded on the dedicated Infusion-Related Reaction eCRF. If a participant experiences both a local and systemic reaction to the same dose of study drug, each reaction should be recorded separately on the Adverse Event eCRF, with signs and symptoms also recorded separately on the dedicated Infusion-Related Reaction eCRF.

1.2. OTHER ADVERSE EVENTS

For AEs other than infusion-related reactions (see Section 1.1), a diagnosis (if known) should be recorded on the Adverse Event eCRF rather than individual signs and symptoms (e.g., record only liver failure or hepatitis rather than jaundice, asterixis, and elevated transaminases). However, if a constellation of signs and/or symptoms cannot be medically characterized as a single diagnosis or syndrome at the time of reporting, each individual event should be recorded on the Adverse Event eCRF. If a diagnosis is subsequently established, all previously reported adverse events based on signs and symptoms should be nullified and replaced by one adverse event report based on the single diagnosis, with a starting date that corresponds to the starting date of the first symptom of the eventual diagnosis.

2. ADVERSE EVENTS OCCURRING SECONDARY TO OTHER EVENTS

In general, AEs occurring secondary to other events (e.g., cascade events or clinical sequelae) should be identified by their primary cause, with the exception of severe or serious secondary events. However, medically significant adverse events occurring secondary to an initiating event that are separated in time should be recorded as independent events on the Adverse Event eCRF. For example:

- If vomiting results in mild dehydration with no additional treatment in a healthy adult, only vomiting should be reported on the eCRF.
- If vomiting results in severe dehydration, both events should be reported separately on the eCRF.
- If a severe gastrointestinal hemorrhage leads to renal failure, both events should be reported separately on the eCRF.
- If dizziness leads to a fall and subsequent fracture, all three events should be reported separately on the eCRF.

All AEs should be recorded separately on the Adverse Event eCRF if it is unclear as to whether the events are associated.

3. PERSISTENT OR RECURRENT ADVERSE EVENTS

A persistent AE is one that extends continuously, without resolution, between participant evaluation time-points. Such events should only be recorded once on the Adverse Event eCRF. The initial severity of the event should be recorded, and the severity should be updated to reflect the most extreme severity any time the event worsens. If the event becomes serious, the Adverse Event eCRF should be updated to reflect this.

A recurrent AE is one that resolves between participant evaluation time-points and subsequently recurs. Each recurrence of an adverse event should be recorded separately on the Adverse Event eCRF.

4. ABNORMAL LABORATORY VALUES

Not every laboratory abnormality qualifies as an adverse event. A laboratory test result should be reported as an adverse event if it meets any of the following criteria:

- Accompanied by clinical symptoms.
- Results in a change in study treatment (e.g., dosage modification, treatment interruption, or treatment discontinuation).
- Results in a medical intervention (e.g., potassium supplementation for hypokalemia) or a change in concomitant therapy.
- Clinically significant in the Investigator's judgment.

It is the Investigator's responsibility to review all laboratory findings. Medical and scientific judgment should be exercised in deciding whether an isolated laboratory abnormality should be classified as an adverse event.

If a clinically significant laboratory abnormality is a sign of a disease or syndrome (e.g., alkaline phosphatase and bilirubin 5 × the upper limit of normal [ULN] associated with cholecystitis), only the diagnosis (i.e., cholecystitis) should be recorded on the Adverse Event eCRF.

If a clinically significant laboratory abnormality is not a sign of a disease or syndrome, the abnormality itself should be recorded on the Adverse Event eCRF, along with a descriptor indicating if the test result is above or below the normal range (e.g., "elevated potassium", as opposed to "abnormal potassium"). If the laboratory abnormality can be characterized by a precise clinical term per standard definitions, the clinical term should be recorded as the adverse event. For example, an elevated serum potassium level of 7.0 mEq/L should be recorded as "hyperkalemia."

Observations of the same clinically significant laboratory abnormality from visit to visit should not be repeatedly recorded on the Adverse Event eCRF, unless the etiology changes. The initial severity of the event should be recorded, and the severity or seriousness should be updated any time the event worsens.

5. ABNORMAL VITAL SIGN VALUES

Not every vital sign abnormality qualifies as an adverse event. A vital sign result should be reported as an adverse event if it meets any of the following criteria:

- Accompanied by clinical symptoms.
- Results in a change in study treatment (e.g., dosage modification, treatment interruption, or treatment discontinuation).
- Results in a medical intervention or a change in concomitant therapy.
- Clinically significant in the Investigator's judgment.

It is the Investigator's responsibility to review all vital sign findings. Medical and scientific judgment should be exercised in deciding whether an isolated vital sign abnormality should be classified as an adverse event.

If a clinically significant vital sign abnormality is a sign of a disease or syndrome (e.g., high blood pressure), only the diagnosis (i.e., hypertension) should be recorded on the Adverse Event eCRF.

Observations of the same clinically significant vital sign abnormality from visit to visit should not be repeatedly recorded on the Adverse Event eCRF, unless the etiology changes. The initial severity of the event should be recorded, and the severity or seriousness should be updated any time the event worsens.

6. ABNORMAL LIVER FUNCTION TESTS

The finding of an elevated ALT or AST in combination with either an elevated total bilirubin or clinical jaundice in the absence of cholestasis or other causes of hyperbilirubinemia is considered to be an indicator of potential severe liver injury.

Therefore, investigators must report as an adverse event the occurrence of either of the following:

- Treatment-emergent ALT or AST $> 5 \times$ ULN value in combination with total bilirubin $> 2 \times$ ULN (of which $\geq 35\%$ is direct bilirubin).
- Treatment-emergent ALT or AST $> 5 \times$ ULN value in combination with clinical jaundice.

The most appropriate diagnosis or (if a diagnosis cannot be established) the abnormal laboratory values should be recorded on the Adverse Event eCRF (see [Appendix 2](#)) and reported to the Sponsor immediately (i.e., no more than 24 hours after learning of the event), either as a serious adverse event or a non-serious adverse event of special interest (see [Section 8.3.6](#)).

7. DEATHS

For this protocol, mortality is an efficacy endpoint. Deaths that occur during the protocol-specified adverse event reporting period (see Section 5 of [Appendix 2](#)) that are attributed by the Investigator solely to progression of cancer should be recorded only on the Death Attributed to Progressive Disease eCRF. All other on-study deaths, regardless of relationship to study treatment, must be recorded on the Adverse Event eCRF and immediately reported to the Sponsor (see Section 5 of [Appendix 2](#)).

Death should be considered an outcome and not a distinct event. The event or condition that caused or contributed to the fatal outcome should be recorded as the single medical concept on the Adverse Event eCRF. Generally, only one such event should be reported. If the cause of death is unknown and cannot be ascertained at the time of reporting, "unexplained death" should be recorded on the Adverse Event eCRF. If the cause of death later becomes available (e.g., after autopsy), "unexplained death" should be replaced by the established cause of death. The term "sudden death" should not be used unless combined with the presumed cause of death (e.g., "sudden cardiac death").

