The PD-1/L1 pathway serves as an immune checkpoint to temporarily dampen the immune response in states of chronic antigen stimulation such as cancer. PD-L1 is an extracellular protein that downregulates immune response through binding to its two receptors, programmed death-1 (PD-1) and B7-1. PD-1 is an inhibitory receptor expressed on T cells following T-cell activation, and expression is sustained in states of chronic stimulation (Blank et al. 2005, Keir et al. 2008). B7-1 is a molecule expressed on antigen-presenting cells and activated T cells. Binding of PD-L1 to PD-1 and B7-1 inhibits T cell proliferation and activation, cytokine production and cytolytic activity, leading to the functional inactivation or exhaustion of T cells (Butte et al. 2007, Yang et al. 2011). Overexpression of PD-L1 on tumor cells has been reported to impede anti-tumor immunity, resulting in immune evasion (Blank et al. 2007), and elevated PD-L1 expression is associated with a worse prognosis. Therefore, interruption of the PD-L1 pathway represents an attractive strategy for restoring tumor-specific T cells immunity. Atezolizumab, which targets the PD-1/L1 pathway, has demonstrated overall survival (OS) benefit across various malignancies, including non-small cell lung cancer (NSCLC).

Treg depletion with PD-L1 pathway blockade

There is accumulating evidence that PD-1 is expressed on activated Treg cells; thus, the activity of Treg cells could be influenced by PD-1/L1 pathway blockade (Wang et al. 2020, Kamada et al. 2019). Administration of an anti-PD-1/L1 agent may increase proliferation and activity of Treg cells, thereby enhancing their suppression activity towards CD4+ and CD8+ T cells. Treg cells present in the tumor microenvironment (TME) would act as a sink towards IL-2, a key proliferative cytokine needed for the expansion of cytotoxic T cells, resulting in a suppressed cytotoxic activity of immune effector cells. Combining RO7296682 (a Treg deplete) and atezolizumab should therefore help restore cancer cell killing via Teffs, by removing one of the resistance mechanisms following the administration of a PD-1/L1 agent.

In preclinical models, RO7296682 has demonstrated the potential to deplete Tregs and therefore enhance T-cell responses against engrafted tumors. In murine tumor models, the survival benefit of the combination of RO7296682 with anti-PD-1/L1 was established and superior to both antibodies when dosed individually.

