3. OBJECTIVES AND ENDPOINTS

The objectives and corresponding endpoints are provided in [Table 4](#).

Note: Due to the adaptive nature of Part III, additional cohorts, which are not described in this protocol, may be added in the study (see [Appendix 6](#), [Appendix 7](#), [Appendix 8](#), and [Appendix 9](#)). For a rationale, see [Appendix 9](#).

Table 4 Objectives and Endpoints

Objectives	Endpoints
Primary	
All Parts (Dose Escalation [Part I] and Dose Expansion [Part II and Part III])	
To evaluate the safety, tolerability, maximum tolerated dose (MTD) and/or recommended Phase 2 dose (RP2D) (Part I only) of RO7296682 when administered in combination with atezolizumab.	
 • Nature and frequency of adverse events (AEs) with severity determined according to NCI CTCAE v5.0 • Nature and frequency of dose-limiting toxicities (DLTs) in Part I
Primary (Dose Expansion Part II and Part III)	
To evaluate the preliminary anti-tumor activity of RO7296682 when administered in combination with atezolizumab.	
 • Objective response rate (ORR) according to RECIST v1.1
Secondary (Dose Escalation, Part I)	
To evaluate the preliminary anti-tumor activity of RO7296682 when administered in combination with atezolizumab.	
 • ORR according to RECIST v1.1
Secondary (Dose-Escalation [Part I] and Dose Expansion [Part II and Part III])	
To further characterize the anti-tumor activity of RO7296682 when administered in combination with atezolizumab.	
 • Disease control rate (DCR) defined as response rate (RR) and stable disease (SD) • Duration of response (DoR) • Progression-free survival (PFS) 
All according to RECIST v1.1
 
 • Overall survival (OS), if data are mature at the time of analysis
To investigate the pharmacokinetic (PK) profile of RO7296682 and atezolizumab after administration of RO7296682 in combination with atezolizumab.	
 • PK profiles and parameters derived for RO7296682 and atezolizumab, as appropriate, including but not limited to: 
 ○ Area under the curve (AUC) ○ Minimum (C_{\min}) and maximum (C_{\max}) concentration ○ Time of maximum concentration (T_{\max}) ○ Volume of distribution at steady-state (V_{ss}) ○ Half-life ($t_{1/2}$)

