1. DEFINITION OF ADVERSE EVENTS

According to the E2A ICH guideline for Good Clinical Practice, an **adverse event** is any untoward medical occurrence in a participant or clinical investigation participant administered a pharmaceutical product and which does not necessarily have to have a causal relationship with this treatment.

An adverse event can therefore be:

- Any unfavorable and unintended sign (including an abnormal laboratory finding), symptom, or disease temporally associated with the use of a medicinal product, whether or not considered related to the medicinal product.

Events Meeting the AE Definition:

- Deterioration in a laboratory value (hematology, clinical chemistry, or urinalysis) or other clinical test (e.g., ECG, x-ray) that is associated with symptoms or leads to a change in study treatment or concomitant treatment or discontinuation from study treatment (see [Appendix 3](#), Section 4).
- Exacerbation of a chronic or intermittent pre-existing condition, including either an increase in frequency and/or intensity of the condition.
- New conditions detected or diagnosed after study treatment administration even though it may have been present before the start of the study.
- Adverse events that are related to a protocol-mandated intervention, including those that occur prior to assignment of study treatment (e.g., screening invasive procedures such as biopsies).
- "Lack of efficacy" or "failure of expected pharmacological action" per se will not be reported as an AE or SAE unless the progression is unexpectedly accelerated and not in line with the natural history of the disease. If the "Lack of efficacy" would not require safety reporting such instances will be captured in the efficacy assessments. However, the signs, symptoms, and/or clinical sequelae resulting from lack of efficacy will be reported as AE or SAE if they fulfill the definition of an AE or SAE.

Events NOT Meeting the AE Definition:

- Any clinically significant abnormal laboratory findings or other abnormal safety assessments which are associated with the underlying disease, unless judged by the Investigator to be more severe than expected for the participant's condition.
- The disease/disorder being studied or expected progression, signs, or symptoms of the disease/disorder being studied, unless more severe than expected for the participant's condition.

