9. LACK OF EFFICACY OR WORSENING OF TUMOR

Events that are clearly consistent with the expected pattern of progression of the underlying disease should not be recorded as adverse events. These data will be captured as efficacy assessment data only. In most cases, the expected pattern of progression will be based on RECIST criteria. In rare cases, the determination of clinical progression will be based on symptomatic deterioration. However, every effort should be made to document progression using objective criteria. If there is any uncertainty as to whether an event is due to progressive disease, it should be reported as an adverse event.

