10. HOSPITALIZATION OR PROLONGED HOSPITALIZATION

Any AE that results in hospitalization or prolonged hospitalization should be documented and reported as a serious adverse event (per the definition of serious adverse event in [Appendix 2](#)), except as outlined below.

An event that leads to hospitalization under the following circumstances should not be reported as an adverse event or a serious adverse event:

- Hospitalization for respite care.
- Planned hospitalization required by the protocol (e.g., for study treatment administration or insertion of access device for study treatment administration).
- Hospitalization for a preexisting condition, provided that all of the following criteria are met:
 - The hospitalization was planned prior to the study or was scheduled during the study when elective surgery became necessary because of the expected normal progression of the disease.
 - The participant has not suffered an adverse event.
- Hospitalization due solely to progression of the underlying cancer.

An event that leads to hospitalization under the following circumstances is not considered to be a serious adverse event, but should be reported as an AE instead:

- Hospitalization for an adverse event that would ordinarily have been treated in an outpatient setting had an outpatient clinic been available.

Appendix 4

Clinical Laboratory Tests

The tests detailed in [Table 1](#) will be performed by the local laboratory and the results must be captured in source documentation and entered into the eCRF. If local laboratory assessments (except for pregnancy test, which must be performed prior to each treatment day with results available prior to dosing) are performed \leq 3 days before the day of the planned dosing, these values can be used and recorded in the eCRF.

Protocol-specific requirements for inclusion or exclusion of participants are detailed in Sections [5.1](#) and [5.2](#), respectively, of the protocol.

Additional tests may be performed at any time during the study as determined necessary by the Investigator or required by local regulations.

Table 1 Protocol-Required Safety Laboratory Assessments

Laboratory Assessments	Parameters
Hematology	
Leukocytes, erythrocytes, hemoglobin, hematocrit, platelets, differential count (neutrophils, eosinophils, basophils, monocytes, lymphocytes, other cells).

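### Appendix 3's rules for deaths and hospitalizations due solely to progression omit the accelerated-progression exception in Appendix 2, so such cases can be missed from AE/SAE counts and 24-hour reporting

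*Combined protocol and SAP*

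**What the plan says.** The rules sit in two appendices. Section 8.3 sends the reader to Appendix 2 for the definitions of AE and SAE and to Appendix 3 for the recording procedures.

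**Appendix 2, Section 1** states the exception twice. Lack of efficacy as such "will not be reported as an AE or SAE unless the progression is unexpectedly accelerated and not in line with the natural history". The list of events that do not meet the AE definition includes "expected progression, signs, or symptoms of the disease/disorder being studied, unless more severe than expected" for that participant. **Appendix 2, Section 2** then says that something which is not an AE under Section 1 cannot be an SAE, and gives death from progression as an example. **Appendix 2, Section 5** requires SAEs to reach the Sponsor within 24 hours.

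**Appendix 3, Section 9** keeps the same limit: "Events that are clearly consistent with the expected pattern of progression of the underlying disease should not be recorded as adverse events". It adds that an event should be reported when it is uncertain whether progressive disease caused it.

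**Appendix 3, Section 7** has no such limit. It says that deaths in the AE reporting period "attributed by the Investigator solely to progression of cancer should be recorded only on the Death Attributed to Progressive Disease eCRF". Every other death on study goes on the Adverse Event eCRF and is reported immediately.

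**Appendix 3, Section 10** lists circumstances in which a hospitalization is to be reported neither as an AE nor as an SAE. The last item is "Hospitalization due solely to progression of the underlying cancer", again without qualification.

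Section 8.3.8, whose title covers disease-related events that do not qualify as AEs or SAEs, reads only that it is not applicable.

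**The concern.** A participant whose tumor progresses much faster than its natural history, and who dies or is hospitalized as a result, falls under two sets of instructions that give opposite answers. Appendix 2 makes the event an AE and, because it is fatal or led to hospitalization, an SAE. Sections 7 and 10 of Appendix 3, read literally, keep it off the Adverse Event eCRF.

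At stake is the primary safety endpoint in all parts, "Nature and frequency of adverse events (AEs) with severity determined according to NCI CTCAE v5.0". An event that is not recorded as an AE is not counted there, is not counted as an SAE and does not trigger a 24-hour report. It also misses the Sponsor's expedited evaluation in Appendix 2, Section 6, which covers SAEs and non-serious AEs of special interest; accelerated progression is not on the special-interest list in Section 8.3.6. The study is open-label and non-randomized, so there is no concurrent control against which an excess would show, and sites that rely on different appendices would record the same event differently.

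**Working it through.** No arithmetic applies. The plan states no figure on this point and gives no rate of accelerated progression. The check is to follow two hypothetical cases through every relevant rule: one participant who dies of unexpectedly accelerated progression, and one who is hospitalized for it and survives. In both, the investigator attributes the event solely to progression.

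| Rule | Fatal case | Hospitalized, survives |
|---|---|---|
| Appendix 2, Section 1 | AE, by the exception | AE, by the exception |
| Appendix 2, Section 2 | SAE: the bar covers only events that are not AEs under Section 1 | SAE, for the same reason |
| Appendix 2, Section 5 | 24-hour report | 24-hour report |
| Appendix 3, Section 7 | separate death eCRF only | does not apply |
| Appendix 3, Section 9 | not exempt: not the expected pattern | not exempt: not the expected pattern |
| Appendix 3, Section 10 | any hospitalization before death is neither AE nor SAE | neither AE nor SAE |
| Section 8.3.8 | no rule | no rule |
| Table 15, summaries of deaths | counted | no entry |
| Overall survival (Section 9.4.2) | counted as an event | not an event |

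Four things follow.

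1. Appendix 2 and the first sentence of Appendix 3, Section 9 agree that both cases are reportable. Sections 7 and 10 are the outliers, so Appendix 3 is inconsistent within itself as well as with Appendix 2.
2. The uncertainty rule in Section 9 does not resolve the conflict. It concerns doubt about whether progression caused the event. Here the cause is accepted, and only the speed is abnormal.
3. Section 10 does refer back to the SAE definition in Appendix 2, but it presents its list as exceptions to SAE reporting. The back-reference therefore does not bring the accelerated-progression exception into the list.
4. The two cases differ in what remains if Section 7 or 10 is followed. The death is still visible in the Table 15 summaries of deaths and in overall survival. The non-fatal hospitalization has no separate safety record. The progression itself would count in progression-free survival, but as an efficacy event.

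**The case against.** The strongest reply is that the documents, read together, already require these cases to be reported. Appendix 2 holds the definitions and states the exception twice. It also asks for signs, symptoms and sequelae of lack of efficacy to be reported when they meet the AE or SAE definition. Appendix 3 is a recording procedure, and its Section 9 exempts only expected-pattern progression. In addition, Sections 7 and 10 apply only when progression is the sole cause; an investigator who suspects that treatment sped up tumor growth could reasonably say that it is not, and Section 7 then requires the Adverse Event eCRF.

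Much of this stands. It rules out the stronger reading that a reader might infer from Sections 7 and 10 alone, namely that these cases necessarily vanish from the primary safety endpoint. They can be missed, depending on which rule a site follows and how the investigator reads the word *solely*. It does not remove the conflict. No text gives the definitions precedence over the more specific instruction with the word *only*, and accelerated progression can still be the sole cause of a death.

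It is also fair to say that a cluster of early progression deaths would be visible elsewhere: on the dedicated eCRF, in Table 15, in overall survival, in the Sponsor and investigators' medical review in Part II, and in the Internal Monitoring Committee's review in Part III. The gap concerns AE/SAE classification and prompt reporting. It does not hide all deaths.

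A reader might further infer that the protocol itself expects accelerated progression with this combination. Section 2.1 says "Administration of an anti-PD-1/L1 agent may increase proliferation and activity of Treg cells, thereby enhancing their suppression activity", and the title of one cited study mentions hyperprogression. The documents do not support that inference. The sentence describes PD-1/L1 blockade, and the same paragraph argues that adding the Treg depleter should remove that resistance mechanism. The reference title is not evidence that can be weighed here.

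Finally, neither appendix gives a growth-rate or time criterion for unexpectedly accelerated progression, so the investigator's judgment decides under any wording. That is correct, and it limits what the fix can achieve.

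**Conclusion.** The contradiction is real but narrow. For a death or hospitalization caused solely by unexpectedly accelerated progression, Appendix 2, Section 1 and Appendix 3, Section 9 point to reporting, while Appendix 3, Sections 7 and 10 point away from it, and no text says which governs. A site following Section 7 or 10 literally would omit the case from AE and SAE counts and from 24-hour reporting. Fatal cases remain in the death summaries and overall survival; non-fatal hospitalizations have no separate safety capture.

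No magnitude is claimed. Any count of affected participants would need a rate of accelerated progression, and the share of such cases attributed solely to progression; the documents give neither. The conclusion rests on the wording alone and on the assumption that some sites will apply the specific recording rule as written. It merits correction because it affects a primary endpoint and the fix is cheap. It is not a flaw in the trial's design.

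**What to change.** Reconcile the passages by carrying the protocol's own exception into the two rules that lack it. In Appendix 3, Section 7, and in the progression item of the first list in Section 10, add a sentence to this effect:

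*This exemption does not apply where the exception for progression in Appendix 2, Section 1 is met; the event is then also recorded on the Adverse Event eCRF and reported as an SAE.*

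Match the eCRF completion guideline to it. Progression that follows the expected pattern stays exempt. Showing these cases on a separate line of the Table 15 output would be convenient but is optional.

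The cost is two sentences in an amendment, a guideline update, a few more SAE reports and a slightly less favorable SAE count. The change removes the contradiction; it does not define how fast is unexpectedly fast, which remains the investigator's judgment.
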